2 OBJECTIVES

We have received 5-year NCI funding to support this study.

The primary objective of this study is to assess the ability of US-guided DOT to reduce the rate of benign biopsy. To achieve this objective we will simultaneously acquire co-registered US imaging data and US-guided DOT imaging data from a group of patients (~300) scheduled for US-guided breast biopsy. We hypothesize that the additional optical information of tHb concentration and distribution will lead to a downgrading of the assessment of a subset of low to moderate suspicion

abnormalities based on conventional imaging (i.e. breast ultrasound with or without mammography) and thereby could lead to a reduction in benign breast biopsies (i.e. false positives).

The secondary and complementary objective is to assess the impact on sensitivity of adjunctive optical data. In particular we hypothesize that by defining a conservative tHb threshold below which malignancy is so rare that the addition of US-guided DOT will not significantly alter the sensitivity of the combined US-guided DOT & CI assessment, i.e. adjunctive US-guided DOT will not decrease true positives.

A third objective is to assess the impact of adjunctive US-guided DOT data in the management of discordant pathology results. In current SOC, the radiologist performing the needle biopsy routinely compares the imaging with the pathology results for concordance. Highly suspicious abnormalities (BI-RAD 4C, 5) that yield benign results are typically considered discordant and are recommended for repeat biopsy or surgical excision. If the discordant abnormality has a tHb below the minimum threshold value, this might allow radiologists to forego a repeat biopsy or surgery. For example, focal fibrosis may appear highly suspicious on US. Our initial data show that fibrotic lesions have low vascularity (28).

Additionally as an exploratory objective, we will compare the results of US-guided DOT and in particular tHb concentration with contrast enhanced mammography (CEM) in the subset of patients who undergo CEM.

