3 ELIGIBILITY CRITERIA

Inclusion Criteria:

- Female subjects \geq 18 years old with ultrasound visible breast abnormalities (BI-RADS 3*, 4A, 4B, 4C, and 5) referred for ultrasound-guided core needle biopsy or fine needle aspiration
- Willing and able to provide informed consent

(*note that while a BI-RADS 3 assessment is probably benign, a subset of patients with this assessment choose to undergo biopsy rather than follow up imaging).

Exclusion Criteria:

- Lesions located in the darkly pigmented nipple-areolar complex area
- Subjects with breast implants
- Abnormality in the mirror image location of the contralateral breast.
- Additional abnormalities in the same region of the breast that would be included in US-guided DOT imaging of the abnormality undergoing biopsy
- Previous breast irradiation of the mirror image location of the contralateral breast
- Lesions located at previous biopsy sites when biopsy occurred within the last six months.
- Pregnancy
- Superficial abnormalities located entirely within (i.e. less than) 5mm of the overlying skin

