7. DATA COLLECTION AND ANALYSIS

Study specific data will be collected from subjects after informed consent is obtained. The following data may be collected on the patient questionnaire: demographic information (name, DOB, Age, Race and Hispanic or Non-Hispanic) MRN#, imaging reports (e.g. mammography, US, PET, MRI, etc.), core biopsy pathology reports, surgical pathology reports if available, breast cancer risk information, etc.

In some cases, the pathologist may review existing biopsy specimens with special staining to look for signs of increased blood supply and vessel density. This will not require additional slicing of standard of care biopsy specimens; thus, samples will not be labeled or stored for the research study. The results of these tests will not be placed in the patient medical record. The results of these tests may be given to the investigators to correlate to the results of the NIR/US procedures.

[figure not shown]
[name], specialist in breast pathology, will assess pathological findings.

The goal of this study is to assess the impact of adjunctive US-guided DOT on the accuracy of breast biopsy recommendations for abnormalities undergoing US-guided breast biopsy. In particular to assess the effect of combining US-guided DOT with CI to: 1. reduce the rate of benign breast biopsy, i.e. decrease false positive biopsy recommendations, and 2. to maintain sensitivity, i.e. maintain true positive recommendations.

Additional goals of this study are to assess the role of US-guided DOT in managing discordant biopsy results and assess the correlation of optical imaging parameters with the presence

and intensity of contrast enhancement of the abnormality undergoing biopsy in patients who have undergone CEM.

Figure 4 – Reader Study Design

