To accomplish the aims of assessing the impact of adjunctive US-guided DOT on reducing benign biopsy recommendation (i.e. FPs), while maintaining sensitivity (i.e. TPs) we will conduct a reader study of the 300 subject trial. Three of four study radiologists will serve as study readers for each case. (To eliminate potential bias a study radiologist performing the biopsy will not serve as a reader for that case.) As noted above the study radiologist who performs or supervises the US-guided DOT exam will be one of the readers. Two additional study radiologist readers will subsequently and independently review the available pre-existing patient information and CI data, (excluding the US-guided biopsy exam) and complete CI and DOT CRFs blinded to the pathology result of the abnormality that underwent biopsy. The CRFs include a BI-RADS assessment. The reader will first complete the CI CRF blinded to the US-guided DOT result, then after reviewing the optical data (tHB concentration and distribution) the reader will complete the DOT CRF including the impact of US-guided DOT information on the BI-RADS assessment, i.e. no change, decreased or increased.

Similar to the CI plus DOT workflow, for cases that have CEM, a CI CRF will be completed first, followed by a CEM specific CRF including a BI-RADS assessment and the impact of CEM on the BI-RADS assessment will be recorded. As noted above, the study radiologist that supervises the US-guided DOT and CEM exams will serve as one of the study readers. For the subsequent two readers we will alternate which adjunctive modality (i.e. CEM or US-DOT) is reviewed first and separate the subsequent review of the second adjunctive modality by a minimum of 4 weeks to prevent recollection bias).

Figure 4 diagrams the core analysis. Combined CI and US-guided DOT BI-RADS 2 and 3 assessments will be considered test negative, and BI-RADS 4A, 4B, 4C, and 5 assessments will be considered test positive. For negative tests, the biopsy proven malignant group (Gc, see Fig. 1(b)) represents false negative results, and the benign group Gd represents true negatives and reflects the potential reduction in benign biopsy recommendation if US-guided DOT were used as SOC. Ga represent true positives and Gb represent false positives utilizing adjunctive US-guided DOT. A comparison of the Ga groups i.e. CI alone vs. CI & DOT will constitute the assessment of the effect of adjunctive US-guided DOT on sensitivity.

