Up to 315 participants will be enrolled to yield 300 participants with valid US-DOT data to evaluate the primary and secondary objectives as below.

Aim 1.1 Assess the impact of US-guided DOT on potential reduction of benign biopsies
The primary objective of this prospective study is to assess the impact of US-guided DOT on the potential reduction of benign biopsies, a.k.a, improve specificity. We hypothesize that the adjunctive use of US-guided DOT will reduce the rate of benign breast biopsy. Using these criteria, the first endpoint, specificity = $Gd/(Gb+Gd)$, will be calculated as the proportion of subjects with a negative assessment (BI-RADS 2 or 3) and with no cancer at biopsy. With the exception of a small minority of patients with BI-RADS 3 assessments who elect to undergo biopsy and who will be tracked separately, all subjects in this study are considered positive using the current SOC, because they have been recommended for biopsy. Hence, 1) the specificity in this group for the SOC is 0% by definition; 2) the estimate of specificity for the DOT system represents the improvement in specificity; and 3) the estimate of specificity is also an indication of the percentage of benign biopsies that might be avoided if the NIR data were used by the radiologist in the biopsy decision making process.

Aim1.2 Assess the impact of US-guided DOT as an adjunct to CI on maintaining high sensitivity
To also ensure that the potential for false negatives is not a significant risk with the use of the US-guided DOT, we will also assess the probability of potentially misclassifying a malignant abnormality. By definition, $FN=Gc/(Gc+Ga)$, which is 1 minus sensitivity. Our earlier study [Zhu reference] indicated that both radiologists reached 96.6% to 100% sensitivity with the tHb data included, and therefore had a 0-3.4% probability of missing a malignant lesion.

All CRFs including CI, DOT, CEM and biopsy results will be entered by our study radiologists, or study coordinator or study pathologist into the OnCore data base to be exported to [name] for statistical analysis. An ad hoc analysis of the CI, CEM and optical imaging characteristics and histopathologic features of false negative cases will be performed to identify suspicious features that always indicate a level of suspicion warranting biopsy.

Aim1.3 Explore the potential benefit of managing post biopsy BI-RADS 4C and 5 lesions

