From a total of 300 patients who undergo the US-DOT exam, we expect to recruit a small subset of patients with BI-RADS 4C or 5 lesions whose biopsy results are benign. We will correlate initial biopsy results, optical data and gold standard final pathology for this subset of patients. This pilot data will allow us to assess the potential benefit of US-guided DOT in managing discordant abnormalities, i.e. reducing additional invasive procedures of a subset of benign abnormalities.

Exploratory Aim 1.4 Explore and compare US-guided DOT and CEM
In this exploratory aim, we will evaluate the agreement (Kappa coefficient) of US-guided DOT and CEM, as both modalities measure alterations in lesion vascularity. We will compare BI-RADS assessments of CI&CEM vs. CI&US-guided DOT as well as correlate imaging data such as intensity of enhancement in CEM and the total hemoglobin level of US-DOT.

Alternative plan: *If US-guided DOT is not comparable with CEM we will evaluate the capability of US-guided DOT in improving the accuracy of combined CI&CEM because CEM may become SOC in a significant subset of patients.*

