We expect ~300 eligible women who will undergo SOC biopsy with valid US-DOT data and fall in the BIRAD categories of 3, 4A, 4B, 4C, or 5, rendering ~210 pathologically benign biopsies and 90 malignant biopsies. **For Study Hypothesis 1**, prior study results indicate the specificity was estimated to be no less than 45%. A total of 83 benign biopsies are needed to achieve 80.18% power to test Study Hypothesis 1 at a 2.5% level. This calculation is based on a 1-sided exact binomial test by conservatively assuming the true specificity is 45%, while 210 benign biopsies achieve 99.4% power to test Hypothesis 1. We also calculated the sample size based on the more stringent requirement that the lower limit of the 1-sided 97.5% conservative Clopper-Pearson binomial exact confidence interval (CI) (60) to the estimated specificity (of 45%) should exceed 30%. The 210 benign biopsies will allow us to estimate the 1-sided 97.5% exact CI to be between 37.7%~100%, thus satisfying this more stringent requirement. **For Study Hypothesis 2**, 90 malignant biopsies will achieve 89.33% power to conduct Study Hypothesis 2 at a 1-sided 2.5% level, based on a 1-sided exact binomial test. With 90 malignant biopsies, the sensitivity can be estimated at 98% with a 1-sided 97.5% exact CI of 92.06%~100%, thus satisfying the stringent criterion requiring a lower limit of >90%.

In calendar year 2016, over 7,000 women came to the Siteman Cancer Center at WashU for diagnostic evaluation. Approximately 17% had suspicious or highly suggestive malignancy findings and were recommended for tissue sampling. Over 700 women underwent US guided biopsy, which is more than 10 times larger than the potential study subjects each year.

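### Truth for sensitivity and specificity is the biopsy result, with no rule for a cancer found later in the index lesion; the consequence falls mainly on the sensitivity test (Aim 1.2).

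*Combined protocol and SAP*

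**What the plan says.** The patients are "referred for ultrasound-guided core needle biopsy or fine needle aspiration" (section 3). Section 7 sets up the cells: "For negative tests, the biopsy proven malignant group (Gc, see Fig. 1(b)) represents false negative results, and the benign group Gd represents true negatives". Under Aim 1.1 in section 7.1, specificity "will be calculated as the proportion of subjects with a negative assessment (BI-RADS 2 or 3) and with no cancer at biopsy". The sample size in section 10.3 is counted the same way, "rendering ~210 pathologically benign biopsies and 90 malignant biopsies". Section 10.4 tests both hypotheses from these cells and has no rule for pathology obtained after the biopsy.

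Elsewhere the protocol recognises that a benign biopsy may not be the last word. Section 2 states: "Highly suspicious abnormalities (BI-RAD 4C, 5) that yield benign results are typically considered discordant and are recommended for repeat biopsy or surgical excision". Section 7 lists among the data that may be collected "core biopsy pathology reports, surgical pathology reports if available". Aim 1.3, which concerns BI-RADS 4C and 5 lesions with benign biopsies, separates the two levels of evidence: "We will correlate initial biopsy results, optical data and gold standard final pathology for this subset of patients".

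**The concern.** The exploratory Aim 1.3 uses a stronger reference standard than the two confirmatory tests, although its patients come from the same 300. One lesion could therefore be malignant in Aim 1.3 and benign in Aims 1.1 and 1.2.

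The case that matters is a cancer missed by the needle and then read as BI-RADS 2 or 3 once the optical data are added. Aim 1.2 exists to count such misses. Under the written rule the lesion falls in Gd and is credited as a benign biopsy that could have been spared. It should be in Gc. Because the sensitivity criterion leaves room for few misses, a small number of such lesions could decide the result. If the rule stays open until the data are seen, the reference standard could also be chosen after the fact.

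**Working it through.** **Inputs.** From sections 10.2 and 10.3: 90 malignant and 210 benign biopsies; null sensitivity 90%, planned 98%; null specificity 30%, planned 45%; one-sided level 0.025; success judged by the one-sided 97.5% Clopper-Pearson lower limit. The number k of lesions benign at the initial biopsy and malignant on later tissue is an assumption, because the documents give no rate.

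**Formulas.** The exact test rejects at the smallest r with P(X ≥ r | n, p0) ≤ 0.025. The lower limit for x successes in n is the 2.5% quantile of Beta(x, n − x + 1).

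**The plan's own figures.**
- Sensitivity, n = 90: r = 87, actual level 0.0169, power at 98% = 89.33% (plan: 89.33%).
- Specificity, n = 83: r = 34, power 80.18% (plan: 80.18%). n = 210: r = 77, power 99.40% (plan: 99.4%).
- Lower limit at 88/90 (97.8%): 92.2% (plan: 92.06% for 98%). The small difference changes nothing.

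The sensitivity criterion therefore allows 90 − 87 = 3 misses: 87/90 has limit 90.6% (pass) and 86/90 has 89.0% (fail).

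**Case A: the k lesions were read BI-RADS 2 or 3 with DOT.** Correct scoring moves them from Gd to Gc. The sensitivity numerator stays and the denominator becomes 90 + k.

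| Scored on biopsy | k | Corrected | Lower limit | Result |
|---|---|---|---|---|
| 88/90 (limit 92.2%) | 1 | 88/91 = 96.7% | 90.7% | pass |
| 88/90 | 2 | 88/92 = 95.7% | 89.2% | fail |
| 89/90 (limit 94.0%) | 2 | 89/92 = 96.7% | 90.8% | pass |
| 89/90 | 3 | 89/93 = 95.7% | 89.4% | fail |
| 90/90 (limit 96.0%) | 3 | 90/93 = 96.8% | 90.9% | pass |
| 90/90 | 4 | 90/94 = 95.7% | 89.5% | fail |

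The critical value for 90 to 97 cancers always leaves exactly 3 misses (for example 88 of 91, 89 of 92, 94 of 97). Over that range the test passes only if the misses already counted plus k come to 3 or fewer.

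Specificity loses k from both numerator and denominator. Starting from 95/210 = 45.2% (limit 38.4%), k = 2 gives 93/208 = 44.7% (limit 37.8%). Even k = 7 gives 88/203 = 43.3% (limit 36.4%), well above 30%.

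**Case B: the k lesions stayed positive with DOT.** Correct scoring moves them from Gb to Ga. With k = 2, sensitivity goes from 88/90 = 97.8% (limit 92.2%) to 90/92 = 97.8% (limit 92.4%), and specificity from 95/210 = 45.2% to 95/208 = 45.7% (limit 38.8%). Here biopsy-only scoring works slightly against DOT on both measures.

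**The case against.** Five points can be made for the plan.

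*The direction is not fixed.* A reader might infer that biopsy-only truth inflates both tests in favour of DOT. The documents do not support that without a condition: it holds in case A and reverses in case B. The one route they describe from a benign biopsy to further tissue is the discordant high-suspicion lesion, whereas downgrading is aimed at low to moderate suspicion (sections 1.1 and 2). Such lesions may therefore seldom reach Gd. This stands and limits the likely size. It does not remove case A, because Aim 1.3 is directed at discordant lesions with low tHb.

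*No surgical gold standard is declared for the trial.* A reader might infer that one is. In fact surgical reports are collected only where available, and the gold-standard label belongs to final pathology in the Aim 1.3 subset. This stands. The point is the missing scoring rule, not a breach of a declared standard.

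*Biopsy may include repeat biopsy, and the figures that show the cells may say more.* The wording for the cells does not say initial, and those figures could not be read in the text available for this review. But the protocol distinguishes repeat biopsy from excision, and initial biopsy from final pathology. At best the rule is ambiguous, and the text should state it.

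*Biopsy result suits the primary endpoint.* Specificity is presented as the share of benign biopsies that could be avoided, so a biopsy-based definition is defensible there, and the conclusion is insensitive to it. This stands for Aim 1.1. It does not carry over to Aim 1.2, which asks whether cancers are missed.

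*Aim 1.3 would bring such cases to light.* It would do so for discordant 4C and 5 lesions, but nothing feeds its result back into the sensitivity test.

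**Conclusion.** The concern holds as a gap in the reference standard that matters mainly for Aim 1.2. The plan scores truth by biopsy and has no rule for a later malignant result on the index lesion, so a cancer missed by both the needle and the reading with DOT can be counted as a true negative.

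At 88/90, close to the planned 98%, one such lesion leaves the sensitivity conclusion intact and two reverse it; from 90/90 it takes four. These counts are illustrations that assume one combined assessment per lesion. The documents give no upgrade rate, so they do not show that a reversal is likely. The specificity conclusion is unaffected in either direction. The plan should be corrected before analysis; its stated power figures are right.

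**What to change.** In sections 7.1 and 10.2, define malignant or benign for Ga to Gd as the worst diagnosis across the initial biopsy, any repeat biopsy and any excision of the index lesion. Use the initial biopsy where no further tissue was taken. Set a cut-off date for later pathology before the analysis begins. Report sensitivity and specificity on initial-biopsy truth as a supporting table, so that the effect of the definition can be seen.

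The cost is wording plus reports that section 7 already lists for collection; no new patients or procedures are needed. There are three downsides: a short wait for later pathology in a few cases, a possibly slightly lower sensitivity, and uneven verification, since later tissue exists only for selected patients. The last should be stated as a limitation.

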A small minority of patients assessed as BI-RADS 3-Probably Benign and recommended for short term follow up imaging on the basis of CI will elect to undergo biopsy. We will separately track the effect of supplemental US-DOT on this small subset.

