9. DATA AND SAFETY MONITORING

In compliance with the Washington University Institutional Data and Safety Monitoring Plan, the Principal Investigator will provide a Data and Safety Monitoring (DSM) report to the Washington University Quality Assurance and Safety Monitoring Committee (QASMC) semi-annually beginning six months after accrual has opened (if at least five patients have been enrolled) or one year after accrual has opened (if fewer than five patients have been enrolled at the six-month mark). This report will include:

- HRPO protocol number, protocol title, Principal Investigator name, data coordinator name, regulatory coordinator name, and statistician
- Date of initial HRPO approval, date of most recent consent HRPO approval/revision, date of HRPO expiration, date of most recent QA audit, study status, and phase of study
- History of study including summary of substantive amendments; summary of accrual suspensions including start/stop dates and reason; and summary of protocol exceptions, error, or breach of confidentiality including start/stop dates and reason
- Study-wide target accrual and study-wide actual accrual

- Protocol activation date
- Average rate of accrual observed in month 1, month 2, and subsequent months
- Expected accrual end date
- Objectives of protocol with supporting data and list the number of participants who have met each objective
- Measures of efficacy
- Early stopping rules with supporting data and list the number of participants who have met the early stopping rules
- Summary of toxicities
- Abstract submissions/publications
- Summary of any recent literature that may affect the safety or ethics of the study

The study principal investigator and Research Patient Coordinator will monitor any potential issues on an ongoing basis. Once the principal investigator or Research Patient Coordinator becomes aware of an adverse event, the AE will be reported to the HRPO and QASMC according to institutional guidelines.

10. Statistical Considerations

10. 1 Study design.

The study consists of two phases. The training phase consists of 20 eligible participants as detailed in Section **“US-guided DOT database and Training”** to assess sources of variabilities. The formal phase is a prospective study to enroll up to 315 eligible participants who will undergo SOC biopsy and fall in the BIRAD categories of 3, 4A, 4B, 4C, or 5 to yield 300 with valid US-DOT data.

10. 2 Study hypotheses and endpoints.

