Study Hypothesis 1 for aim 1.1: The first hypothesis is that the measured tHb distribution and values can be potentially used as an adjunct for radiologists to reduce unnecessary biopsies in low risk patients with benign pathological results. The benign biopsy spare rate can be calculated as $Gd/(Gb+Gd)$ in Fig.11, which is equivalent to the specificity, the primary endpoint of Aim1.1. We observed in previous studies that specificity could be improved by 45% on average if NIR data were used in the decision-making process. Note that the specificity in this group of biopsied patients under the SOC is 0% by definition. In this study, we conservatively set the minimum acceptable specificity at 30%. The null and alternative hypotheses, which demonstrate superiority when the NIR imaging data are used as an adjunct to the diagnostic assessment versus when the SOC diagnostic data are used alone, are given by

$$H_0: \text{Specificity} \leq 30\% \text{ versus } H_1: \text{Specificity} > 30\%$$

This aim will be considered a success if the lower limit of the 95% confidence interval on specificity exceeds 30%. This hypothesis will be tested at the one-sided 0.025 level, rather than 0.05, to account for the fact that two hypothesis tests (on specificity and sensitivity) are planned. This aim is considered a success if the lower limit of the 97.5% confidence interval on specificity exceeds 30%.

Study Hypothesis 2 for aim 1.2: The second hypothesis is that, while reducing unnecessary benign biopsies, the addition of adjunct information from US-DOT still maintains a high sensitivity

in capturing nearly all malignant tumors. This can be evaluated based on sensitivity, which is calculated as $G_a/(G_a+G_c)$, as shown in Fig.11.

H_0 : sensitivity $\leq 90\%$ versus H_1 : sensitivity $> 90\%$

Based on previous study, we anticipate the sensitivity will be in the range of 96-100%. This aim is considered a success if the lower limit of the 95% confidence interval for sensitivity is at least 90%. This hypothesis will be tested at the one-sided 0.025 level, rather than 0.05, to stringently account for the fact that two hypothesis tests (on specificity and sensitivity) are planned. This aim is considered a success if the lower limit of the 97.5% confidence interval for sensitivity is at least 90%.

10.3 Sample size justifications.

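### Combined CI+DOT specificity is reported as the improvement due to DOT, but the 0% baseline describes the biopsy referral, not the readers' own CI-alone reads

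*Combined protocol and SAP*

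**What the plan says.** Section 7.1, Aim 1.1, defines the primary endpoint as Gd/(Gb+Gd): among lesions benign at biopsy, the proportion with a combined CI and DOT assessment of BI-RADS 2 or 3. It takes standard-of-care specificity as 0% because the subjects had been recommended for biopsy, and infers that "the estimate of specificity for the DOT system represents the improvement in specificity". Section 7 says in the same spirit that "the benign group Gd represents true negatives and reflects the potential reduction in benign biopsy recommendation if US-guided DOT were used as SOC". Section 10.2 tests the endpoint against a fixed 30% and describes this as showing "superiority when the NIR imaging data are used as an adjunct to the diagnostic assessment versus when the SOC diagnostic data are used alone".

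The reader study in section 7 produces a second, different baseline. Three study radiologists read each case. "The reader will first complete the CI CRF blinded to the US-guided DOT result", and each CRF carries a BI-RADS category. The DOT CRF then records "the impact of US-guided DOT information on the BI-RADS assessment, i.e. no change, decreased or increased". For sensitivity, section 7 uses this pairing: "A comparison of the Ga groups i.e. CI alone vs. CI & DOT will constitute the assessment" of the effect on sensitivity. No matching comparison is stated for specificity. Section 10.4 lists a one-sample exact test and a Clopper-Pearson limit for each hypothesis.

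For women assessed as BI-RADS 3 who choose biopsy, section 7 says "We will separately track the effect of supplemental US-DOT on this small subset", and Aim 1.1 repeats the exception. Section 10.1 nevertheless describes participants who "fall in the BIRAD categories of 3, 4A, 4B, 4C, or 5 to yield 300 with valid US-DOT data", and section 10.3 derives the roughly 210 benign biopsies from that total. Section 10.2 restates the 0% without the exception, and section 10.4 analyses all evaluable subjects.

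**The concern.** The 0% and the endpoint come from different assessments. The 0% describes the clinical decision that brought the woman to biopsy. The endpoint describes what study readers conclude, two of whom review the case afresh. Nothing in the plan requires a reader's CI-alone category to be 4A or higher. If a reader calls a benign lesion 3 on CI and records no change after DOT, the lesion enters Gd although DOT did nothing. Combined specificity equals the improvement due to DOT only if readers never call a benign lesion 2 or 3 on CI alone (or if such calls are exactly offset by DOT upgrades).

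The primary objective is the effect of adding DOT. As written, the trial would publish combined specificity as the share of benign biopsies avoided because of DOT, and would claim superiority over conventional data from a test that contains no CI-alone result.

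**Working it through.** **Inputs from the plan.** Null specificity 30%, one-sided level 0.025 (10.2); assumed true specificity 45%, about 210 benign biopsies (10.3); exact binomial test (10.4).

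**The plan's own figures.** Take the smallest r with P(X ≥ r | n, 0.30) ≤ 0.025, then power = P(X ≥ r | n, 0.45).

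- n = 83: r = 34, size 0.0218, power 80.18%, as stated.
- n = 210: r = 77 (36.7%), size 0.0225, power 99.4%, as stated.

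The arithmetic of Hypothesis 1 is sound. The question is what the number measures.

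**Decomposition.** Let f be the share of benign lesions that readers call 2 or 3 on CI alone. The net DOT increment is combined specificity minus f. The documents do not give f, so 5 to 20% is an assumed range.

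| f (assumed) | Increment at the success boundary, 36.7 − f | Increment at the planned 45%, 45 − f | Share of the reported 45% not due to DOT, f/45 |
|---|---|---|---|
| 5% | 31.7 points | 40 points | 11% |
| 10% | 26.7 points | 35 points | 22% |
| 15% | 21.7 points | 30 points | 33% |
| 20% | 16.7 points | 25 points | 44% |

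At the boundary, the increment falls below 30 points once f exceeds 36.67 − 30 = 6.67%, which is 14 of 210 lesions.

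**Chance of declared success when the true DOT increment is 20 points.** This is P(X ≥ 77 | 210, 0.20 + f): below 0.1% at f = 0, 2.2% at f = 10%, 33.0% at 15% and 85.5% at 20%.

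**BI-RADS 3 at enrolment.** Suppose k of the 210 benign lesions were enrolled as BI-RADS 3, all stay 2 or 3 after DOT (an upper bound, since DOT can raise the assessment), and 45% of the rest are negative. Reported specificity is (0.45 × (210 − k) + k)/210: 46.3% for k = 5 and 47.6% for k = 10. Both counts are assumptions.

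**The case against.** The best counter-argument concerns size.

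- **f may be close to zero.** Section 5 says the radiologists who perform or supervise the DOT exam are not blinded to clinical data, and the other two readers see pre-existing patient information. Readers may rarely depart from the referral category. At f = 1 to 2%, the boundary increment is 35.7 to 34.7 points. This stands, and it is why f should be measured rather than set to zero by definition.
- **The 45% may already be a DOT effect.** Section 1.1 describes it as the share of benign 4A and 4B lesions that could have been spared. Combined specificity would then be f + 0.45(1 − f), and the increment 0.45(1 − f) = 42.8, 40.5, 38.3 and 36.0 points for f = 5, 10, 15 and 20%, always above 30. This is a fair alternative, although section 10.3 applies 45% to the combined endpoint. It still leaves f/[f + 0.45(1 − f)] = 10, 20, 28 and 36% of the reported figure not due to DOT.
- **The boundary is an unlikely result.** If true specificity is 45%, 77 or fewer negatives occur with probability 0.9%. The 30% is also a bar for combined specificity, not for the increment. And with no DOT effect at all, f would have to exceed 30% for success to be more likely than 2.5%. All correct: the test is protected, the attribution is not.
- **BI-RADS 3 cases are tracked separately.** That rule follows the assessment at enrolment. It does not cover a reader who downgrades a referred 4A or 4B lesion on CI, and section 10 does not carry it through.
- **Figure 4 is not shown.** It may include CI-alone groups, but the text names a comparison only for sensitivity.

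**Conclusion.** The concern holds. Item 2 of the argument in Aim 1.1 and the superiority wording in section 10.2 are wrong as written. The hypothesis test against 30%, its size and its power are unaffected. What is not identified is the improvement due to DOT and the share of benign biopsies it would avoid.

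The overstatement equals f, less any CI-negative benign lesions that DOT moves up. Over the assumed 5 to 20% it is 5 to 20 points, or 11 to 44% of a reported 45% (10 to 36% if 45% is the rate among CI-positive lesions). If f is 1 or 2%, it is 1 or 2 points. The logic is certain; the size depends on a rate the documents do not supply. It should be fixed before the reader data are analysed.

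**What to change.** 1. Keep the section 10.2 test of combined specificity against 30%. In Aim 1.1 (item 2) and section 10.2, delete the statement that this specificity is the improvement due to DOT and the wording that the test shows superiority over standard-of-care data alone.
2. In section 10.4, estimate the improvement as the within-reader paired difference, specificity(CI+DOT) minus specificity(CI alone), with a confidence interval clustered by patient because three readers read each case. Also report CI-alone specificity and the share of CI-positive benign lesions downgraded to 2 or 3.
3. Base any superiority claim over CI alone on the lower limit of that difference exceeding 0, tested only after Hypothesis 1 succeeds, so that no alpha is split. This leaves the success rule as it is; it changes what success is said to show.
4. State in section 10 that lesions enrolled as BI-RADS 3 are outside Gb+Gd in the primary analysis and are reported separately.
5. As a matter of completeness, list the paired sensitivity comparison from section 7 in section 10.4.

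**Cost.** SAP wording and one added analysis from CRFs already collected. If 10 BI-RADS 3 lesions are excluded, 200 benign lesions remain: success at 74 of 200, size 0.0200, power 99.1% at 45%. With one read per lesion and no DOT upgrades, the 95% half-width of the paired difference d = 0.45 − f is 1.96 × √[(d − d²)/200]: 6.8, 6.6, 6.4 and 6.0 points for f = 5, 10, 15 and 20%. If DOT moves 2% of lesions up, it is 6.6 to 7.3 points. Power to show a difference above 0 exceeds 99% throughout (simulated one-sided exact McNemar test at 0.025). The drawback is that the improvement credited to DOT may be smaller than the headline specificity.
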